4.7.4.2 CCI Analysis for Missing Data

In order to assess the potential impact of missing data on the results of the primary efficacy analysis, Copy Reference and Tipping Point CCI analyses using multiple imputation (MI) will be performed on all mITT subjects based on the approach proposed by Keene et al. [1].

Since Promis II was curtailed early, not all subjects are expected to have 365 days follow-up as intended in the original trial design. The expected duration of exposure for some subjects will therefore be shorter than 365 days. Therefore, and prior to unblinding, the expected duration of exposure in years, t_j , will be determined for each subject, $n = 1 \dots j$, individually using their randomisation date, r_j , and the date of study closure, d , where $d = 28\text{FEB}2022$ and $t_j = \min([d - r_j + 1]/365.25, 365/365.25)$. For all subjects with a realised follow-up duration, f_j , shorter than t_j , ie. with $f_j < t_j$, for example, due to early withdrawal or dropout

CONFIDENTIAL

Sponsor:	Zambon S.p.A.	Protocol Number:	Z7224L02
----------	---------------	------------------	----------

at time f_j relative to randomisation, the number of pulmonary exacerbations in the missing period of follow-up, $t_j - f_j$, will be imputed.

The number of potentially missing exacerbations per subject will be imputed to include the following variables: treatment, country, as detailed in Section 4.9.1, and use of stable concomitant therapy with oral macrolides.

The imputation will be performed according to the following strategies:

- (1) Copy reference: imputation of missing data in both randomised treatment groups based on the data distribution of data observed in the placebo group. This analysis mimics the case where discontinued subjects who were randomised to colistimethate sodium are assumed to instantaneously transition to placebo and lose any effect conferred by colistimethate sodium.

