- (2) Tipping Point Analysis. For this analysis, discontinued subjects who were randomised to colistimethate sodium or placebo are initially imputed assuming the best case that data are missing at random and the treatment effect, CI and p-value are extracted. The analysis is subsequently repeated but now applying a small detrimental effect, δ , in the imputation of colistimethate sodium subjects with missing data and, again, the treatment effect, CI and p-value are extracted. This analysis is then repeated with an increasing penalisation of colistimethate sodium treated subjects by addition of a detrimental effect, 2δ , 3δ , ..., $k\delta$ in order to find the 'Tipping Point' being that degree of penalisation that leads to loss of statistical significance on the primary endpoint analysis.

A total of 20 imputed datasets will be generated with each analysed using the same NB model as described for the primary analysis. Log event rate and log event rate ratio estimates and associated SEs arising from these 20 imputed datasets will then be combined via PROC MIANALYZE using Rubin's rules ^[2].

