SET dataset4act_mar dataset4plb;
BY Iteration Subject;
RUN;

DATA dataset4all_cr; /* For Copy Reference */
SET dataset4act_cr dataset4plb;
BY Iteration Subject;
RUN;

DATA dataset5_mar; /* Missing at Random */
SET dataset4all_mar;
BY Iteration Subject;
ARRAY c[*] c_psite_d1-c_psite_dx c_med_d;
ARRAY x[*] psite_d1-psite_dx med_d;
k=1/Dispersion;
imp_subj=(years<365/365.25);
years_imp=MAX(years,years_exp);
log_years_imp=LOG(years_imp);
linpred_1=.;
IF imp_subj THEN DO;
years_miss=years_imp-years;
linpred_1=Intercept;
DO i=1 TO DIM(c);
linpred_1+c[i]*x[i];
END;
linpred_mar=linpred_1+c_treatment_d*treatment_d;
y2hat_mar=years_miss*EXP(linpred_mar);
CALL STREAMINIT(3231212);
y2_mar=RAND('NEGBINOMIAL',k/(k+y2hat_mar),k);
y_imp_mar=count+y2_mar;
END;
ELSE DO;
y_imp_mar=count;
END;
RUN;

DATA dataset5_cr; /* Copy Reference */
SET dataset4all_cr;
BY Iteration Subject;
ARRAY c[*] c_psite_d1-c_psite_dx c_med_d;

```

CONFIDENTIAL

Sponsor:	Zambon S.p.A.	Protocol Number:	Z7224L02
----------	---------------	------------------	----------

```

ARRAY x[*] psite_d1-psite_dx med_d;
k=1/Dispersion;
imp_subj=(years<365/365.25);
years_imp=MAX(years,years_exp);
log_years_imp=LOG(years_imp);
linpred_1=.;
IF imp_subj THEN DO;
  years_miss=years_imp-years;
  linpred_1=Intercept;
  DO i=1 TO DIM(c);
    linpred_1+c[i]*x[i];
  END;
  linpred_cr=linpred_1+c_treatment_d;
  y2hat_cr=years_miss*EXP(linpred_cr);
  CALL STREAMINIT(3231212);
  y2_cr=RAND('NEGBINOMIAL',k/(k+y2hat_cr),k);
  y_imp_cr=count+y2_cr;
END;
ELSE DO;
  y_imp_cr=count;
END;
RUN;

```

Notes:

- dataset1 includes one record per patient;
- count represents the total number of **CCI** t;
- treatment represents the treatment group (treatment order: 1 = colistimethate sodium, 2 = placebo);
- treatment_d represent the dummy variables for treatment group (values of the dummy variables: 0 for colistimethate sodium; 1 for placebo);
- Psite represents the country, as detailed in Section 4.9.1;
- psite_d1-psite_dx represent the dummy variables for the country;
- Med represents use of stable concomitant therapy with oral macrolides (e.g. azithromycin or erythromycin or clarithromycin) (Yes/No);
- med_d represents the dummy variable for use of stable concomitant therapy with oral macrolides;
- years represents the observed follow-up time in years;
- years_exp represents the expected follow-up time in years
- log_years represents the logarithm of the follow-up time in years.

Analysis step

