The imputed dataset obtained using the above SAS code will be finally analysed and the results will be combined.

```

ODS OUTPUT LSMMeans=lsmmeans_mar Estimates=ratios_mar; /* Missing at Random */
PROC GENMOD DATA=dataset5_mar;
  BY Iteration;

```

CONFIDENTIAL

Sponsor:	Zambon S.p.A.	Protocol Number:	Z7224L02
----------	---------------	------------------	----------

```

CLASS treatment psite med;
/* MAR imputation */
MODEL y_imp_mar = treatment psite med/ OFFSET=log_years_imp DIST=NEGBIN;
LSMEANS treatment / ilink cl diff exp om;
ESTIMATE 'Col. Sodium / Placebo' treatment 1 -1 / exp;
RUN;

DATA lsmeans_mar2;
SET lsmeans_mar (WHERE=(zValue ne .));
BY Iteration;
IF first.Iteration THEN _Imputation_+1;
IF _Imputation_ LE 1000;
RUN;

ODS OUTPUT ParameterEstimates=lsmeans_mar3;
PROC MIANALYZE PARMS=lsmeans_mar2;
CLASS treatment;
MODELEFFECTS treatment;
RUN;

DATA lsmeans_mar4;
SET lsmeans_mar3;
exp_est=EXP(Estimate);
exp_lcl=EXP(LCLMean);
exp_ucl=EXP(UCLMean);
RUN;

DATA ratios_mar2 (RENAME=LBetaEstimate=Estimate);
SET ratios_mar (WHERE=(ChiSq ne .));
BY Iteration;
IF first.Iteration THEN _Imputation_+1;
IF _Imputation_ LE 1000;
Effect='Label';
RUN;

ODS OUTPUT ParameterEstimates=ratios_mar3;
PROC MIANALYZE PARMS =ratios_mar2;
CLASS Label;
MODELEFFECTS Label;
RUN;

DATA ratios_mar4;
SET ratios_mar3;
exp_est=EXP(Estimate);
exp_lcl= EXP (LCLMean);
exp_ucl= EXP (UCLMean);
RUN;

```

CONFIDENTIAL

Sponsor:	Zambon S.p.A.	Protocol Number:	Z7224L02
----------	---------------	------------------	----------

```

ODS OUTPUT LSMeans=lsmeans_cr Estimates=ratios_cr; /* Copy Reference */
PROC GENMOD DATA=dataset5_cr;
  BY Iteration;
  CLASS treatment psite med;
  /* CR imputation */
  MODEL y_imp_cr = treatment psite med/ OFFSET=log_years_imp DIST=NEGBIN;
  LSMEANS treatment / ilink cl diff exp om;
  ESTIMATE 'Col. Sodium / Placebo' treatment 1 -1 / exp;
RUN;

```

```

DATA lsmeans_cr2;
  SET lsmeans_cr (WHERE=(zValue ne .));
  BY Iteration;
  IF first.Iteration THEN _Imputation_+1;
  IF _Imputation_ LE 1000;
RUN;

```

```

ODS OUTPUT ParameterEstimates=lsmeans_cr3;
PROC MIANALYZE PARMS=lsmeans_cr2;
  CLASS treatment;
  MODELEFFECTS treatment;
RUN;

```

```

DATA lsmeans_cr4;
  SET lsmeans_cr3;
  exp_est=EXP(Estimate);
  exp_lcl=EXP(LCLMean);
  exp_ucl=EXP(UCLMean);
RUN;

```

```

DATA ratios_cr2 (RENAME=LBetaEstimate=Estimate);
  SET ratios_cr (WHERE=(ChiSq ne .));
  BY Iteration;
  IF first.Iteration THEN _Imputation_+1;
  IF _Imputation_ LE 1000;

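### The imputation step labelled missing at random ignores each patient's own exacerbation count, so the tipping-point analysis need not start from the primary result

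*SAP*

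**What the plan says.** SAP 4.7.4.2 plans two multiple-imputation analyses, copy reference and tipping point. On the imputation model it says: "The number of potentially missing exacerbations per subject will be imputed to include the following variables: treatment, country", with macrolide use as the third variable. The patient's own count is not listed. In the tipping-point analysis, patients who discontinue "are initially imputed assuming the best case that data are missing at random", and growing penalties are then applied to the colistimethate arm.

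The example code in SAP 4.14 fits a negative binomial model to each arm separately. It sets `k` to the reciprocal of the dispersion and computes `y2hat_mar` as missing time multiplied by the exponentiated linear predictor. It then draws "y2_mar=RAND('NEGBINOMIAL',k/(k+y2hat_mar),k" and adds the observed count. The completed total is analysed with "MODEL y_imp_mar = treatment psite med/ OFFSET=log_years_imp DIST=NEGBIN".

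SAP 4.11 says the primary model relies on MAR and that the analyses of 4.7.4.2 examine its conclusion when data are missing not at random.

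On the number of imputations, 4.7.4.2 says "A total of 20 imputed datasets will be generated", while the code keeps results under "IF _Imputation_ LE 1000".

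**The concern.** In a negative binomial model each patient has a latent rate, and the observed count is evidence about it. A patient with two exacerbations in six months is expected to have more in the next six than a patient with none. The coded draw gives both the same expected number. It treats the two periods as independent within a patient, while the analysis step fits one negative binomial to their sum.

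MAR allows withdrawal to depend on exacerbations already seen. The primary likelihood respects that dependence; the coded draw does not.

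Withdrawal after exacerbations is possible here. Protocol 9.7 says an exacerbation does not require discontinuation but lets the investigator discontinue the patient, and Protocol 15 lists adverse events and investigator discretion among the reasons.

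What is at stake is the reading of the tipping point. The penalty should be counted from a MAR start equal to the primary result. If the start has already moved, the reported tipping point mixes an artefact of the draw with the penalty.

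**Working it through.** **Inputs.** Placebo rate 1.09 per year, 170 completers per group, two-sided 0.05, power 90% at a 35% reduction and 80% at 30%, about 20% withdrawal (Protocol 3, Sample Size). 287 randomised, so about 143 per arm (SAP 3.9). The planned variances are redacted; the over-dispersion is described only as mild (Protocol 19.3, SAP 3.9).

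**1. Implied dispersion.** From a Wald test of the log rate ratio with one common dispersion:

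dispersion = [170·(ln RR)²/(z₀.₉₇₅ + z_power)² − 1/1.09 − 1/(1.09·RR)]/2

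- RR 0.65, 90%: (3.002 − 0.917 − 1.411)/2 = 0.337
- RR 0.70, 80%: (2.755 − 0.917 − 1.311)/2 = 0.264

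The single value 0.30 gives powers of 90.7% and 79.0%, so it reproduces both stated figures closely.

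**2. Correct conditional draw.** Let y1hat and y2hat be the model means for the observed and missing periods. Given the observed count, the missing count is negative binomial with size k + count and mean y2hat·(k + count)/(k + y1hat). The code uses size k and mean y2hat.

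Example: a placebo patient leaves at six months, dispersion 0.30, so k = 3.333 and y1hat = y2hat = 0.545.

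- Code: 0.545, whatever the history
- Conditional, two exacerbations: 0.545 × 5.333/3.878 = 0.749
- Conditional, none: 0.545 × 3.333/3.878 = 0.468

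**3. What the coded step estimates.** With one rate per arm, 12 months' expected follow-up and parameters at their estimates, the arm rate is s·(events/exposure) + (1 − s)·(model rate), where s is the share of expected time observed. At s near 0.9 this is mostly the simple rate of SAP 4.7.4, which is sound only if withdrawal is unrelated to exacerbations. In one run of pattern (d) below, the placebo arm gives 0.878 × 1.0506 + 0.122 × 1.0910 = 1.0555, against a model rate of 1.0910.

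**4. Why the conditional draw works.** With M = y1hat + y2hat, (count + E[y2] − M)/(k + M) = (count − y1hat)/(k + y1hat). At the primary estimates each patient's completed-data score equals the primary score, for any covariates and any expected follow-up. In 2,000 simulated trials of 143 per arm with a common dispersion, the largest difference from the primary log rate ratio was 0.0003.

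**5. Size.** Large-sample shift in the log rate ratio, coded step minus primary, true ratio 0.65, 12 months' expected follow-up, no covariates:

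| Withdrawal pattern | disp. 0.26 | 0.30 | 0.34 |
|---|---|---|---|
| (a) 20%, unrelated to exacerbations | 0.000 | 0.000 | 0.000 |
| (b) 10% unrelated plus 10% after each exacerbation, both arms | +0.004 | +0.005 | +0.005 |
| (c) as (b), but 15% active and 10% placebo after each exacerbation | 0.000 | 0.000 | 0.000 |
| (c) reversed | +0.010 | +0.011 | +0.012 |
| (d) 25% after each exacerbation, both arms, no other withdrawal | +0.009 | +0.010 | +0.011 |
| (e) 25% after each exacerbation, active only | −0.020 | −0.023 | −0.026 |
| (e) 25% after each exacerbation, placebo only | +0.029 | +0.033 | +0.037 |

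The conditional draw shifts by at most 0.0004 in every pattern. The standard error at 143 per arm is about 0.15, so at 0.30 the shift is 0.010/0.15 = 0.07 SE in (d) and 0.15 to 0.22 SE in (e). Simulated trials of 143 per arm at 0.30 gave mean shifts of 0.000 (a), +0.004 (b), +0.009 (d), and −0.022 and +0.032 (e). Raising active-only withdrawal to 40% after each exacerbation, with about 20% unrelated withdrawal on placebo, gave about −0.035.

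With no true effect at 0.30 the shift is 0.000 in (a), (b) and (d), 0.006 either way in (c) and 0.033 either way in (e). At dispersion 1.0, an assumed upper bound that would not be mild, it is +0.015 in (b), +0.030 in (d), and −0.075 or +0.104 in (e).

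**The case against.** The strongest reply is that this hardly matters. The primary analysis does not use the code. The shift is zero when withdrawal is unrelated to exacerbations and about 0.03 SE in the mixed case (b). When both arms behave alike, it moves the ratio towards 1, against the drug. A shift in favour of colistimethate larger than 0.006 needs exacerbation-driven withdrawal in the active arm only, and nothing in the documents suggests that. Exacerbation is not itself a listed withdrawal reason. The closure date in SAP 4.7.4.2 shortens expected follow-up for late entrants, which trims the extreme figures slightly. All of this stands, and it limits the weight of the point.

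A second reply is that the code is only an example, that 4.7.4.2 cites a published method which may itself condition on the count, and that the tipping-point code is not shown. These are real limits: I have not used the paper, and I assume the tipping point uses the same draw. They do not settle the matter, because the SAP's own text names three variables and the only code it gives leaves the count out.

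A third is that the MAR estimate is reported before any penalty, so a gap from the primary would be visible. It would, but nothing in the output would tell the reader that the draw caused it.

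**Conclusion.** The concern holds. The step labelled MAR is inconsistent with the negative binomial model fitted before and after it, and it need not reproduce the primary estimate when withdrawal follows exacerbations. The expected effect is small: 0.000 to about +0.012 in log rate ratio in the patterns where exacerbations drive withdrawal in both arms, and roughly −0.02 to +0.04 in the one-arm extreme with 25% withdrawal after each exacerbation. It would seldom change the conclusion by itself.

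The reading of the code is certain. The size rests on the inferred dispersion of 0.26 to 0.34 and would grow if the observed dispersion were larger. The point should be corrected because it is cheap and gives the tipping point a clean origin; it does not threaten the primary result.

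**What to change.** 1. In the MAR and tipping-point steps, compute y1hat as observed time multiplied by the exponentiated linear predictor. Draw the missing count with success probability (k + y1hat)/(k + y1hat + y2hat) and size k + count. Apply any tipping-point penalty to y2hat only.
2. Take the parameters for these steps from one model of both arms with a treatment term and a common dispersion, as in the primary analysis. With separate fits, the conditional draw is centred on the primary (mean within 0.002) but scatters around it at 143 per arm (SD 0.011 in (b), 0.030 in (d)). This addresses scatter, not bias.
3. State in SAP 4.7.4.2 that the draw is conditional on the patient's observed count and follow-up through this distribution, not by adding them as regression covariates. If the marginal draw is intended, say so, give the reason, and do not call it MAR without qualification.
4. For copy reference, condition on the count as well, and state whether the observed period uses placebo or own-arm parameters. One sentence points to the first ("imputation of missing data in both randomised treatment groups based on the data distribution of data observed in the placebo group") and the next to the second ("assumed to instantaneously transition to placebo and lose any effect conferred by colistimethate sodium"). The choice is the sponsor's; at dispersion 0.30 and ratio 0.65 the two differ by only about 0.005 in log rate ratio.
5. Separately, give one number of imputations in both places.

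The cost is a few SAS lines, one joint fit in place of two for the MAR step, and short text edits. No new data are needed, but it must be done before unblinding.

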5.1 Table Format

All output will be produced using SAS version 9.4 or a later version.

- All TFLs will be produced in landscape format on American letter size, unless otherwise specified.
- All TFLs will be produced using the Courier New font, size 8, which is the smallest acceptable point size for the Regulatory Authorities.
- The data displays for all TFLs will have a minimum blank 1-inch margin on all 4 sides.
- Headers and footers for figures will be in Courier New font, size 8 which is the smallest acceptable point size for the Regulatory Authorities.
- Legends will be used for all figures with more than 1 variable, group, or item displayed.
- TFLs will be in black and white (no colour).
- Specialized text styles, such as bolding, italics, borders, shading, and superscripted and subscripted text, will not be used in the TFLs, unless otherwise specified. On some occasions, superscripts 1, 2, or 3 may be used (see below).
- Only standard keyboard characters will be used in the TFLs. Special characters, such as non-printable control characters, printer-specific, or font-specific characters, will not be used. Hexadecimal-derived characters will be used, where possible, if they are appropriate to help display math symbols (e.g., μ). Certain subscripts and superscripts (e.g., cm^2 , C_{max}) may be employed on a case-by-case basis.
- Mixed case will be used for all titles, footnotes, column headers, and programmer-supplied formats, as appropriate.

Headers

- All output should have the following header at the top left of each page:

Zambon Protocol Z7224L02 (CCI ██████████ CCI ██████████)

- All output should specify the Draft/Final Run status at the top centre of each page.

CONFIDENTIAL

Sponsor:	Zambon S.p.A.	Protocol Number:	Z7224L02
----------	---------------	------------------	----------

- All output should have Page n of N at the top right corner of each page. TFLs are internally paginated in relation to the total length (i.e., the page number should appear sequentially as page n of N, where N is the total number of pages in the table).
- The date output was generated should appear along with the program name as a footer on each page.

Display Titles

- Each output is identified by the designation and a numeral. (i.e., Table 14.1.1). ICH E3 numbering is strongly recommended. A decimal system (x.y and x.y.z) is used to identify TFLs with related contents. All titles will be centre-aligned. The analysis population will be identified on the line immediately following the title. The output number and title will be single-line spaced. A solid line spanning the margins will separate the display titles from the column headers. There will be one blank line between the last title and the solid line.

Table x.y.z
 First Line of Title
 Second Line of Title if Needed
 (mITT Population)

In a listing, in the case that a subject's record has been continued to the next page, an appropriate identification (e.g., the subject ID number) must be presented at the beginning of that page.

5.2 Conventions

Unless otherwise specified, in summary tables of continuous variables, the minimum and maximum values will be displayed to the same number of decimal places as the raw data, the mean and median will be presented to one extra decimal place compared to the raw data, and the standard deviation will be displayed to two extra decimal places compared to the raw data. Wherever possible data will be decimal aligned.

Unless otherwise specified, frequency tabulations will be presented by number and percentage, where the percentage is presented in brackets to 1 decimal place. Percentages between 0.05% and 0.1% will be rounded to 0.1%. Percentages less than 0.05% will be displayed as <0.1%. Percentages between 99.90% and 99.95% will be rounded to 99.9%. Percentages more than 99.95% will be displayed as >99.9%.

P-values, if applicable, will be presented to 5 decimal places. If the p-value is less than 0.00001 then it will be presented as <0.00001. If the rounded result is a value of 1.00000, it will be displayed as >0.99999.

Any date information in the listing will use the *date9*. format, for example, 07MAY2002. In the listing, a unit associated with a variable will be presented only once within parentheses either below or next to that variable in the heading portion.

CONFIDENTIAL

Sponsor:	Zambon S.p.A.	Protocol Number:	Z7224L02
----------	---------------	------------------	----------

Unless otherwise specified, listings should be sorted by treatment group, subject and visit and have the source ADaM dataset referenced in a footnote.

All tables, listings and figures will be converted into Rich text format with the format/file extension specified and collated into three separate complete documents. The combined documents will be in .pdf format.

CONFIDENTIAL

Sponsor:	Zambon S.p.A.	Protocol Number:	Z7224L02
----------	---------------	------------------	----------

5.3 Tables

5.3.1 Section 14.1: Demographic and Baseline

Table 14.1.1.1	Subject Disposition	(Screened Subjects)
Table 14.1.1.2	Subject Disposition by Country	(ITT Population)
Table 14.1.1.3	Subject Disposition by Visit	(mITT Population)
Table 14.1.2.1	Inclusion/Exclusion Criteria Deviation	(Screened Subjects)
Table 14.1.2.2	Protocol Deviations Affecting Analysis Populations	(Screened Subjects)
Table 14.1.2.3	Protocol Deviations Related to COVID-19	(Screened Subjects)
Table 14.1.3	Analysis Populations	(Screened Subjects)
Table 14.1.4.1	Demographics	(mITT Population)
Table 14.1.4.2	Demographics	(Safety Population)
Table 14.1.5	Smoking and Alcohol Status	(mITT Population)
Table 14.1.6	Non-CF Bronchiectasis History	(mITT Population)
Table 14.1.7	Medical History	(mITT Population)
Table 14.1.8	Spirometry at Visit 1 and Pre-Dose at Visit 2: FEV ₁ and FVC	(mITT Population)
Table 14.1.9	Presence of P. aeruginosa in Sputum at Visit 1	(mITT Population)
Table 14.1.10.1	Number and Duration of Inhaled Doses	(Safety Population)
Table 14.1.10.2	Number and Duration of Inhaled Doses	(mITT Population)
Table 14.1.11.1	Exposure Days and Extent of Exposure	(Safety Population)
Table 14.1.11.2	Exposure Days and Extent of Exposure	(mITT Population)
Table 14.1.12	IMP Adherence	(mITT Population)
Table 14.1.13.1	IMP interruptions	(Safety Population)
Table 14.1.13.2	IMP interruptions	(mITT Population)
Table 14.1.14.1	Prior Medication	(mITT Population)
Table 14.1.14.2	Concomitant Medication	(mITT Population)

